### 11.1 Sample size

The complete population implanted with I1 (N = 16) will be screened for participation in the investigation and the estimated sample size will be 12-14 patients enrolled, about 15% drop-out, and approximately 11 patients completing the study. Data from 11 patients will enable detection of a statistically significant difference between aided and non-aided functional gain of 9 dB or higher (based on normal approximation), with 90% power, 5% two-sided level of significance, and an estimated variability (SD) for the difference of 8 dB. This is considered well within the clinically relevant detection levels for functional gain as described by the systematic literature review on comparable devices [F]. The proposed sample size is also considered to ensure clinically relevant data for conclusions on the secondary end-point SSQ12, where the previous study on the I1 and S2 [A] has used a sample size of 10 patients, and 11 patients would enable detection of statistically significant differences in mean scores of 1 or higher (based on normal approximation), with 90% power, 5% two-sided level of significance, and an estimated variability (SD) for the difference of 0.9.

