#### 8.1.1 Primary hypothesis

**Hypothesis 1A:** The hypothesis for the primary objective is that there will be a significant improvement in subjects' aided thresholds with the Sentio 1 compared to unaided. The investigation will be declared successful if the primary endpoint is statistically significant (i.e., the null hypothesis H0 is rejected in favor of the alternative hypothesis H1) according to the following hypothesis.

- H0: Same or higher (worse) PTA4 with Sentio 1 compared to unaided.
- H1: Lower (better) PTA4 with Sentio 1 compared to unaided.

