## 11 STATISTICAL DESIGN AND ANALYSIS

The statistical analysis of all efficacy variables will be performed according to the study Statistical Analysis Plan. The general methodology for the analysis of primary, secondary, and tertiary endpoints is described below. Wilcoxon signed-rank test will be used to test hypotheses. The decision of the hypothesis test is done at the 5% significance level. Pearson's correlations (or Spearman's if the data is not normally distributed) will be used to test correlations.

The distribution of continuous variables will be given as Mean, 95% confidence interval (CI) of the mean, standard deviation (SD), Minimum and Maximum (Mean (SD), (Min; Max)). The distribution of categorical and dichotomous variables will be given as number and percentage (n = (%)).

All subjects that consented to the investigation will be included in the safety population; all subjects enrolled and treated in the investigation will be included in the Intent-to-Treat (ITT) population. All subjects included in the investigation with no major protocol deviations will be included in the Per-Protocol (PP) population. The final decisions regarding the PP population will be taken after investigation completion, at the Clean File meeting before the database lock. All efficacy analyses will be performed on the PP population as main analysis. Complementary analysis for all efficacy variables will also be performed on the ITT population.

Details will be described in the Statistical Analysis Plan.

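### Does the stated 90% power at two-sided 5% with 11 completers fit the planned Wilcoxon test, the directional hypothesis and the enrolment range?

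*Combined protocol and SAP*

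**What the plan says.** Section 11.1 rests the sample size on the paired difference between unaided and aided thresholds: "Data from 11 patients will enable detection of a statistically significant difference between aided and non-aided functional gain of 9 dB or higher", "with 90% power, 5% two-sided level of significance, and an estimated variability (SD) for the difference of 8 dB". It describes the basis as a normal approximation. It makes a parallel statement for SSQ12: a difference of 1 point, SD 0.9, with the same power and the same two-sided 5%. The recruitment plan is "12-14 patients enrolled, about 15% drop-out, and approximately 11 patients completing the study", drawn from the 16 people who have the implant. Section 9.3.3 says that subjects who leave are not replaced.

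Section 11 names the analysis: "Wilcoxon signed-rank test will be used to test hypotheses". It sets the threshold: "The decision of the hypothesis test is done at the 5% significance level". It gives no sidedness there, takes the per-protocol set as the main analysis, and leaves details to a Statistical Analysis Plan.

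Section 8.1.1 states the hypotheses directionally, "H0: Same or higher (worse) PTA4 with Sentio 1 compared to unaided" against "H1: Lower (better) PTA4 with Sentio 1 compared to unaided", and makes success depend on rejecting the null.

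**The concern.** The power statement, the test and the success rule seem to describe three different procedures.

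- **Method.** A plain normal formula at 11 subjects does not return 9 dB. It also treats the SD as known, and the test actually planned is a rank test.
- **Numbers.** The bottom of the enrolment range, less 15%, falls short of 11. Subjects who leave are not replaced, and per-protocol exclusions could lower the number further.
- **Sidedness.** A directional hypothesis decided at an unqualified 5% can be read as a one-sided 5% test. That would roughly double the favourable-direction error assumed in planning.

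Section 6.2 calls the investigation confirmatory, and this is its only success criterion. If the figures were materially wrong, the investigation could be underpowered, or success could be declared on weaker evidence than planned.

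**Working it through.** **Inputs (section 11.1).** Difference 9 dB, SD 8 dB; SSQ12 difference 1 point, SD 0.9; two-sided alpha 0.05; power 90%; 12 to 14 enrolled; drop-out 15%. Test from section 11: Wilcoxon signed-rank.

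**1. The plan's own figure.**

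Plain normal formula: n = [SD × (1.960 + 1.282) / difference]².
- 9 dB: [8 × 3.2415 / 9]² = 8.3, so 9 subjects.
- SSQ12: [0.9 × 3.2415 / 1]² = 8.5, so 9 subjects.
- Detectable at n = 11: 3.2415 × 8 / √11 = 7.8 dB, and 3.2415 × 0.9 / √11 = 0.88 points. Power at 9 dB and 1 point is 96.2% and 95.8%.

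Paired t-test (normal differences, SD estimated; noncentral t with n − 1 degrees of freedom and noncentrality √n × difference / SD):

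| n | 9 dB | 1 SSQ12 point |
|---|---|---|
| 10 | 88.5% | 87.7% |
| 11 | 91.9% | 91.2% |
| 12 | 94.3% | 93.8% |

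Eleven is the smallest n that reaches 90% for both. The differences detectable at exactly 90% are 8.69 dB and 0.98 points, which round to the stated 9 and 1. So the stated figures match a paired t calculation, and the remark in "functional gain of 9 dB or higher (based on normal approximation" makes sense as an assumption of normally distributed differences. Under the stricter z-formula reading, the stated figures are conservative.

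**2. The planned test.** Exact Wilcoxon critical values, with power simulated from normal differences (300,000 samples or more per cell), two-sided 5%:

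| n | 9 dB | 1 SSQ12 point |
|---|---|---|
| 9 | 78.5% | 77.3% |
| 10 | 87.0% | 86.1% |
| 11 | 89.1% | 88.3% |
| 12 | 92.1% | 91.4% |

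At 11 the shortfall from 90% is 0.9 points for the primary endpoint and 1.7 points for SSQ12. The difference detectable at 90% is about 9.1 dB and 1.03 points.

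**3. Enrolment.** 12 × 0.85 = 10.2; 13 × 0.85 = 11.05; 14 × 0.85 = 11.9. Enrolment needed for 11 completers is 11 / 0.85 = 12.9, so 13, the midpoint of the stated range.

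**4. Sidedness.** With 11 untied differences there are 2¹¹ = 2048 equally likely sign patterns under the null. Let W− be the rank sum of the unfavourable differences.
- Two-sided 5% (2.5% per tail): reject when W− ≤ 10, probability 43/2048 = 2.1%.
- One-sided 5%: reject when W− ≤ 13, probability 85/2048 = 4.2%.

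The two readings differ only when W− is 11, 12 or 13, which has null probability 42/2048 = 2.05%. For a true gain of 9 dB, one-sided power at n = 11 is 94.8% against 89.1% two-sided. The ambiguity therefore affects error, not loss of power.

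**5. Larger gains (illustrative, SD 8).** Two-sided Wilcoxon power at n = 10 is 98.3% for 12 dB and 99.9% for 15 dB.

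**The case for a change.** The strongest argument for a change is the success rule. Sections 8.1.1 and 11, read without section 11.1, allow a one-sided 5% test, and a confirmatory criterion should have one reading. One sentence would settle it at no cost, and the same edit could restate power for 10 to 12 completers under the test actually planned. The Wilcoxon test does first reach 90% at 12 evaluable subjects. The per-protocol set could also fall below 11; at 9 subjects, two-sided power for 9 dB is 78.5%.

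What stands is the omission: section 11 gives no sidedness beside a directional hypothesis. Yet section 11.1 specifies two-sided 5% for both endpoints, and nothing in the protocol says one-sided. The consistent reading is a two-sided 5% test with success only if the difference favours the device. The Statistical Analysis Plan to which section 11 defers is the usual place to write this down; it is not part of the text available here.

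The rest does not stand as an error. Planning under normality and analysing with a rank test is common practice, section 11.1 states its basis openly, and the cost at 11 is one to two points. The drop-out shortfall arises only at the lowest enrolment, in a sentence that hedges both the drop-out rate and the number of completers. The primary endpoint is measured at one month, so attrition over two years probably overstates the loss for it. Nine evaluable subjects is possible, but that would mean more loss than the plan assumes, and rewording the power statement would not add subjects.

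**Conclusion.** No change is needed. The stated 90% is not materially wrong on any reasonable reading: at 11 subjects and two-sided 5%, power for 9 dB is about 96% by the normal formula, 91.9% by paired t and 89.1% by exact Wilcoxon. The lowest enrolment figure leaves about 10 completers, with Wilcoxon power of 87% for 9 dB and 86% for one SSQ12 point. Recruitment cannot be extended freely, because all 16 people with the implant are already to be screened.

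The missing sidedness is a gap that analysts would fill sensibly from section 11.1. Filling it that way keeps the favourable-tail error at 2.1% with 11 subjects. The alternative reading, at 4.2%, has no positive support in the text and would alter the conclusion only for a rank sum of 11 to 13.

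This rests on normal differences without ties or zeros, on the protocol's SDs of 8 dB and 0.9 points, and on the two-sided level in section 11.1 governing the test. The conclusion would need another look if the separate Statistical Analysis Plan set a one-sided 5% test.

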### 11.2 Timing for data analysis

One interim data analysis will be performed when all subjects have completed the second visit. The interim data analysis will include all investigation end-points at that time point. A final analysis will be made after all subjects have finalized the last visit and conclude on the safety assessment.

Data cleaning and database lock of the applicable data will be performed both before the interim analysis and prior to the final data analysis. Data cleaning activities and database lock procedures will be defined in a data management plan prior to investigation start.

### 11.3 Missing data handling

Missing data (e.g., single questions, experimental repetitions) will be treated as Not A Number (NANs) and will be disregarded from the analysis. A detailed description of missing data will be given in the Statistical Analysis Plan. Missing data will be handled in the same way for PP and ITT population.

oticon MEDICAL	Title Clinical Investigation Plan BC114	Document no Doc-00117705	Revision 4	Page 26(39)
--------------------------	---	------------------------------------	----------------------	-----------------------

## 11.4 Reporting deviations from the original statistical analysis plan

Any deviations discovered throughout the investigation from the original SAP, will be described with justification in a CIP amendment to the final report, as deemed appropriate.

## 11.5 Subgroups for analysis

No analysis on subgroups will be performed in the investigation.

## 12 DATA MANAGEMENT

Data management will be conducted according to the investigation specific Data Management Plan (DMP). Any deviations, i.e., discrepancies and additions from the process defined in the DMP will be described in an investigation specific database lock meeting minutes.

All personal data collected and processed concerning the subjects participating in the investigation are protected under the Regulation (EU) 2016/679 (GDPR) and will be handled accordingly. Further, professional secrecy regarding subject information and data applies to all involved personnel, including Sponsor representatives.

Names and/or other explicit personal identification information will not be collected or recorded for investigational purposes, with one crucial exception: it is the responsibility of the investigator to keep a 'Subject Identification Log' up to date, where personal identification information matches the Subject Identification Number (see below). The 'Subject Identification Log' must be kept up to date and stored in the Investigator Site File (ISF) in a secure location with restricted access. This log will not, at any time during and after the investigation, be available to any unauthorised party, nor available in the Sponsor files.

All subjects enrolled in the investigation will be provided with a Subject Identification Number (i.e., pseudonymization), consisting of a digit code, where the leading digit represents the investigation site number, for this single-site investigation all subject ID number will start with 100 and the two following numbers represents the consecutive subject number (e.g. 101 for the first enrolled subject 102 for the second enrolled subject).

### Source documents

Source documents shall be created and maintained by the investigation site team as per clinical routine throughout the investigation. Source documents are the original records, including but not limited to worksheets (e.g., printouts of eCRF forms), physician or nursing notes, subject questionnaires etc. During each visit where printouts or copies of the source documentation are used for the investigation, these shall be signed and dated (i.e., certified) by a member of the investigation site team.

For investigation-specific variables, a possibility to use a combined worksheet/checklist will be made available to the investigation site. These worksheets will then, if used, constitute the source for the data noted in the worksheets. The site will store the worksheets in the ISF. The Sponsor may request a copy for remote monitoring. For variables entered directly into the eCRF, the eCRF is considered the source. To ensure consistency in the recording of source data, the use of worksheets versus entering data directly into the eCRF will be defined based on the preferred workflow of the site (if not directly entered into the medical record).

A source data agreement list will be created at each investigation site to define which are the source documents for the data gathered in the study and the location of them. This document will be completed at the first interim monitoring visit at the latest.

The Principal Investigator will provide direct access to source data during and after the clinical investigation for monitoring, audits, and regulatory authority review and inspections, if applicable. Permission for this

direct access to source documents needs to be obtained by the investigator from the subjects, hospital administration and local regulatory authorities as applicable, before starting the clinical investigation.

### **Case Report Form recording and processing**

Data captured will be recorded, by the investigator and/or delegated site staff, in eCRFs by means of an EDC-system (SMART-TRIAL), provided/hosted by an external party (MEDEI ApS, Copenhagen, Denmark). The system has built-in features that enables users to be GCP and GDPR compliant. All data in relation to SMART-TRIAL is stored on secured Microsoft Azure hardware located in the EU, i.e., Dublin, Ireland. All users of the EDC system have personal accounts, accessed by two-factor authentication, allowing tracking of all data entries and changes in the system (i.e., audit trail).

The set-up, build and maintenance of the eCRF, incl. corresponding content (forms, events, data checks etc.), and testing/validation of the system, is performed by trained Sponsor representatives.

All data, subject- and product-related, must be accurately recorded in a timely manner (i.e., within 5 working days) into the EDC system by the delegated site staff.

NB. For Serious Adverse Events (SAE), Serious Adverse Device Effects (SADE) stricter timelines applies, see Section 18.4 for further reference.

The person entering the data into the database is not allowed to make any personal interpretation or to make any decisions on the data than self-evident corrections as listed in the data entry instructions or data handling report. All entered data must be consistent with the source documents, and if any discrepancies are found they must be corrected or explained in writing where applicable. The Principal Investigator is responsible for the data entered in the EDC-system and for signing the eCRF at the end of the clinical investigation.

The patient reported outcome (PRO) instrument used in this investigation will be completed on paper forms by the subjects themselves. The forms (i.e., source documents), marked with the Subject ID, will then be transferred by manual data entry to the corresponding form in the EDC-system by an authorized member of the investigation site team.

For screening failures following data will be recorded: reason for failure with reference to IE criteria and patient characteristics.

### **Data Management**

To ensure data validity and accuracy, manual data cleaning and query handling will be performed remotely on a regular basis within the EDC-system. In addition, computerized edit checks will be utilised for identifying data values that are outside the allowed range, incomplete or inconsistent, and CIP deviations. The Data Validation Plan (DVP) specifies the checks that are to be performed on subject data for the clinical investigation.

Once all data has been captured and entered into the eCRF by the investigation site team, verified and validated by the appointed Sponsor representatives, and all reconciliation with the reported events and events reported to Oticon Medical Research and Development department, the clinical investigation database will be locked and the data will be analysed.

### **Storage of data**

The investigator should retain clinical investigation records for at least 15 years after completion (or premature termination) of the investigation, or, in the event that the device is subsequently placed on the market, at least 15 years after the last corresponding device has been placed on the market. However, it is the responsibility of the investigator to make sure that the investigation record of clinical investigation subjects is retained in accordance with local legislation and in accordance with the maximum period of time allowed by the hospital. The investigator will continue having 'view access' to the study database even after

study closure.

The Principal Investigator must take measures to prevent accidental or premature destruction of these documents and at the end of the storage period, acquire a confirmation from the Sponsor before proceeding with the destruction of the documentation.

If the principal investigator leaves the investigation site, he/she will provide the Sponsor with the name and address of the person who will resume responsibility for the ISF. If the ISF will be transferred to another party (e.g., external archive, service provider etc.) this shall be discussed, agreed and documented in beforehand between the investigation site and the Sponsor.

The complete study database, which is a part of the TMF, will be securely stored at Oticon Medical, with restricted access. The TMF will be retained for 15 years after completion (or premature termination) of the investigation, or in the event that the device is subsequently placed on the market, at least 15 years after the last corresponding device has been placed on the market.

#### **Missing data**

Handling of missing data will be described in the SAP. In order to minimize missing data, the importance of complete follow up data sets will be emphasized to investigators and investigation site staff, as will the importance of recruiting subjects who are motivated to undergo treatment and participate in the investigation. The investigation site is leading in the field of bone conduction devices, thus familiar with the outcomes of the treatment, and what level of treatment compliance that can be expected from patients considering undergoing treatment with a device. The sites will also have experience in conducting clinical investigations and recruiting investigation subjects. The patient information will give the subjects a clear understanding of the design of the investigation and the visit schedule. The latter has been carefully considered to mimic the standard practice of treatment with a bone conduction device, but also to be feasible in relation to the burden on the investigation subjects as a mitigation measure to avoid drop-outs and/or missing appointments. In addition, subjects will be given the opportunity to complete out PROs at the applicable site visits if they have forgotten to bring them or to complete them on beforehand.

Monitoring through the electronic data capturing system will be performed all through the investigation period. Early and close monitoring of the eCRFs will enable the Sponsor to take action and get back to site if missing data and/or deviations are found. The Sponsors representatives will be in close contact to site to give support and training for general quality assurance of the data captured in the investigation

#### **Audits and inspections**

Audits of the clinical investigation may be conducted by the Sponsor or third parties designated by the Sponsor to evaluate compliance with the CIP, written procedures, this International Standard and the applicable regulatory requirements. These audits may cover all involved parties, systems and facilities and are independent of, and separate from, routine monitoring or quality control functions.

### **13 AMENDMENTS TO THE CIP**

If changes to the CIP are needed, proposed amendments to the CIP shall be agreed upon between the Sponsor and Principal Investigator, and/or the coordinating investigator. Substantial amendments should be approved by the EC and Competent Authority (CA), as applicable, before incorporated.

In addition, substantial amendments to the Subject Information and Consent Form and/or other applicable documents previously approved by the EC/CA must be approved by the EC/CA before they will come into effect. For non-substantial amendments, local regulations regarding notifications to EC/CA should be followed.

	Title Clinical Investigation Plan BC114	Document no Doc-00117705	Revision 4	Page 29(39)
---	---	------------------------------------	----------------------	-----------------------

## 14 DEVIATIONS FROM CLINICAL INVESTIGATION PLAN

A CIP deviation is an intentional or unintentional failure to follow the requirements of the CIP. Every effort should be made to comply with the requirements of the CIP and the Investigator, and other representatives of the investigational site team, is not allowed to deviate from the CIP, unless needed to protect the rights, safety and well-being of the subjects (i.e., emergencies). Under these circumstances, deviations from the CIP may proceed without prior approval by the Sponsor and favourable opinion from EC. Such cases should be documented and reported to the EC, as per local requirements, and to the Sponsor as soon as possible, but in no event later than 5 working days after the emergency occurred.

If other deviations occur, the Investigator should inform the monitor/clinical trial manager and make a record in the CIP Deviation Log provided in the EDC system. The implications of the deviation must be reviewed and discussed between the Sponsor and the Investigator. If deviations are found during monitoring visits, they should also be documented in the monitoring report and handled as above. This should be done as soon as possible after detection to avoid repetitive deviations. Continuous review of protocol deviations during monitoring visits aim to detect systematic errors and to identify retraining needs at the site. Frequency of monitoring is described in the monitoring plan and should be increased if systematic deviations are identified. All protocol deviations must be documented stating the reason, date, the action(s) taken, and the impact for the subjects and/or the investigation. If serious or repeated deviations occur, the Sponsor has the right to initiate early termination of the investigation.

At the end of the investigation, or in connection to a predefined interim analysis, protocol deviations will be re-categorized as minor or major and their consequence on analysis populations will be determined.

